Investigational Product: Type, Dose and Mode of Administration	
Reltecimod is the sodium acetate salt of a 10-amino acids synthetic peptide that is homologous to specific amino acid residues of the T-lymphocyte receptor CD28.
 
Reltecimod is packaged in glass vials as a lyophilized powder to be reconstituted with 10.5 mL of sterile water for injection (WFI) to a concentration of 1 mg/mL. Each vial contains 10.5 mg of Reltecimod with an excipient to protect the peptide during the lyophilization process. Sterile WFI should be obtained by the site pharmacy.
 
The dose of Reltecimod will be 0.50 mg/kg, administered as a one-time dose, with drug administration initiated within the 6-hour time-window from the diagnosis of SA-AKI, only after the decision is made by the attending surgeon at the study site for a surgical or interventional radiology procedure for the abdominal infection or after confirmed diagnosis of abdominal infection has been established by a surgical or interventional radiology procedure; or after surgical confirmation of NSTI as described in the inclusion criteria.
 
Drug will be reconstituted on the day of its administration, in close proximity to infusion time, and several vials will be pooled together to compose the requested dose. Drug will be administered as an intravenous infusion, separate from other medications, over 10 minutes using a syringe pump (may be manually pushed if approved by the medical monitor). Volume of administration will be dependent on the patients' actual weight plus adequate priming volume of the IV line.
 
Placebo for Reltecimod is pyrogen-free and preservative-free sterile 0.9% sodium chloride solution, USP. This should be obtained by the local pharmacy. The volume of blinded placebo should be calculated similarly as for the active group according to the patient's actual body weight (0.50 mL/kg), plus adequate priming volume of the IV line.

---	--

Flow Chart

Study design from clinical presentation to study drug administration for patients with abdominal infection or necrotizing soft tissue infection and confirmed Stage 2 or 3 AKI.

Study Visits		
	Visit	Study Day
	1	Screening
	2	Day 1 Begins with study drug administration and ends with the same calendar day
	3	Day 2
	4	Day 3
	5	Day 7 (± 1 day)
	6	Day 10 (± 1 day) Perform only if patient is still hospitalized
	7	Day 14 (± 1 day)
	8	Day 21 (± 1 day)
	9	Day 29 (+3 days)
	10	3 to 21 Days after Visit 9

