7.3 Schedule of Procedures/Visits

A schedule of study assessments is shown in Section 18-Appendix A (“Study Visits and Procedures”) of the protocol. Homecare services will be offered through a third party vendor (i.e., Symphony Clinical Research) using trained, qualified homecare professionals. Provision of this service is intended to help ensure patient retention and data collection when travel to the clinical trial sites may be overly burdensome for the participants given their disease state. Symphony Clinical Research is contracted to evaluate subjects as outpatients from Day 7 through Day 90.

Local laboratories will be used during hospitalization and clinic visits while the home health service will send samples to a central laboratory. Outpatient samples may be evaluated by other local laboratories if acceptable accreditation.

Patients who are registered and randomized for the study, but do not receive study drug (part of the Intent-to-Treat (ITT) population) should continue to be followed through Day 90 with as much data collected as part of SOC entered into the eCRF. No additional procedures or laboratory studies should be performed beyond SOC as part of the research study. The entered data will match as closely as possible the SoC assessments and laboratory evaluations with the visit days.

Visit 1: Screening

Evaluation starts once a patient presents with clinical diagnosis of abdominal infection.

- Obtain ICF
- Verification of Inclusion/Exclusion criteria
- Demographics, medical history, infection history, concomitant medications, vital signs, height, weight, physical exam (PE). Race is not entered for European countries.
- Record urine output from presentation or around (before) time of diagnosis of abdominal infection or NSTI recorded to study drug administration or until 48 hour window to develop Stage 2 or 3 AKI ends
- Record serum creatinine values every 6 hours from presentation or around (before) time of diagnosis of abdominal infection until study drug administration or until 48 hour window to develop Stage 2 or 3 AKI ends (blood draws may be adjusted to when blood is normally collected on the unit)
- Determine kidney size by CT or renal ultrasound if patient does not have a reference creatinine value within the past 12 months
- Recording baseline signs and symptoms and AEs/SAEs (AEs of Screening are AEs/SAEs starting after obtaining ICF until study drug administration)
- Safety baseline laboratory tests:

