- Concomitant medications
- Critical care parameters (dates and times of assisted ventilation, vasopressor use, ICU /hospital stay)
- Collect blood for systemic inflammatory biomarkers - leukocyte transcriptome (RNA expression) profiling and chemokine / cytokines at 72±4 hours post study drug administration – optional sub-study (Day 4 only)
- Record survival

Visit 5 (Day 7 [±1 day])

- Fluid balance (total I/O) for calendar day
- Detailed urine output
 - Should be recorded continuously from time of study drug administration to Day 7 (if still in ICU or step down unit (or equivalent), using most frequent hourly intervals available and by calendar day with or without Foley catheter in place
- Collect data on additional amputations if NSTI
- Collect data on acute RRT
- Record additional relevant procedures related to the kidney (e.g., renal biopsy)
- Record any imaging that evaluates the kidney
- Weight (if easily obtained)
- Collection of AEs/ SAEs including secondary infections
- Record any follow-up surgical or interventional radiologic procedures for previously documented abdominal infection or NSTI
- Concomitant medications
- Vital signs (to be taken during the morning tests)
- PE (visiting nursing service does not perform if outpatient)
- Standard CRP
- Spot urine for albumin to creatinine ratio
- Safety laboratory tests
 - Full chemistry panel (see Section 9.2.11)
 - CBC with differential and platelet count
- Critical care parameters (dates and times of assisted ventilation, vasopressor use, ICU /hospital stay)
- Record any hospital re-admissions (if previously discharged for original sepsis-related hospitalization)

- Systemic response: collect data for SOFA parameters
 - All efforts should be made to obtain the actual measurements of SOFA parameters at these visits-may use SpO2 value (and record FiO2) if arterial blood gas is not clinically indicated.
 - Platelet count, creatinine and total bilirubin values required for SOFA components can be obtained from safety laboratories performed at this visit.
- Assess lesion status if NSTI (healing/progression/significant change in appearance) if accessible for visible assessment at time of debridement or routine dressing change
- Collect urine and blood for plasma for storage (AKI biomarker analysis) – optional sub-study
- Record Survival

Visit 6 (Day 10 [±1 day]; perform only if patient is still hospitalized)

- Concomitant medications
- Collection of AEs/SAEs, including secondary infections

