- Collect data on additional amputations if NSTI
- Collect data on acute RRT
- Record additional relevant procedures related to the kidney (e.g., renal biopsy)
- Record any imaging that evaluates the kidney
- Record any follow-up surgical or interventional radiologic procedures for previously documented abdominal infection or NSTI
- Symptom-driven interim PE
- Vital signs (to be taken during the morning tests)
- Critical care parameters (dates and times of assisted ventilation, vasopressor use, ICU /hospital stay)
- Record any hospital re-admissions (if previously discharged for original sepsis-related hospitalization)
- Serum creatinine
- Assess lesion status if NSTI (healing/progression/significant change in appearance) if accessible for visible assessment at time of debridement or routine dressing change
- Record Survival

Visit 7 (Day 14 [±1 day])

- Weight
- Collection of AEs/SAEs, including secondary infections
- Collect data on acute RRT
- Record additional relevant procedures related to the kidney (e.g., renal biopsy)
- Record any imaging that evaluates the kidney
- Record any follow-up surgical or interventional radiologic procedures for previously documented abdominal infection or NSTI
- Concomitant medications

- Safety laboratory tests (Chemistry, Hematology)
 - Full chemistry panel (see Section 9.2.11)
 - CBC with differential and platelet count
- Spot urine for albumin to creatinine ratio
- PE (visiting nursing service does not perform if outpatient)
- Vital signs (to be taken during the morning tests if still hospitalized)
- Standard CRP
- Collect blood for serum for storage (immunogenicity testing)
- Critical care parameters (dates and times of assisted ventilation, vasopressor use, ICU /hospital stay)
- Record any hospital re-admissions (if previously discharged for original sepsis-related hospitalization)
- Systemic response: collect data for SOFA parameters
 - All efforts should be made to obtain the actual measurements of SOFA parameters at these visits-may use SpO₂ value (and record FiO₂) if arterial blood gas is not clinically indicated.
 - Platelet count, creatinine and total bilirubin values required for SOFA components can be obtained from safety laboratories performed at this visit.
 - In case a patient is discharged from hospital prior to these days SOFA parameters should be obtained on the same day of discharge.

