3.8 Clinical Laboratory Assessments

Safety laboratory investigations will include results of hematology labs (CBC including platelets and white blood cell differential), and of blood chemistry labs (Glucose; Electrolytes (Sodium, Potassium, Chloride, Bicarbonate, Calcium, Phosphorus); Renal function tests (Urea/BUN, Serum Creatinine); Liver function tests (Albumin, Bilirubin Total, Alanine transaminase (ALT), Aspartate

transaminase (AST), Alkaline phosphatase (ALP); Total Protein). Also, urine albumin / creatine ratio will be evaluated.

Pregnancy testing will be done on all women of childbearing potential participating in the study (using the quicker of a blood test or urine test).

Clinical laboratory assessments will be collected at intervals according to time and events in Section 18.1 of the Clinical Trial Protocol.

Hematology will be collected at Screening, Day 1, Day 3, Day 7, Day 14, and Day 29.

Blood chemistry will be collected at Screening, Day 1 (bilirubin and creatinine only), Day 2 (creatinine only), Day 3 (bilirubin and creatinine only), Day 7, Day 10 (creatinine only), Day 14, Day 21 (creatinine only), Day 29 (albumin and creatinine only), 3 to 21 days after Day 29 visit (creatinine only), and at 3 months (creatinine only). The standard C-Reactive Protein (CRP) test (not the high sensitivity-hsCRP) will be used to evaluate inflammatory response and will be obtained at Screening and Days 7, 14, and 29.

Urine will be collected at Screening, Day 1, Day 3, Day 7, Day 14, Day 29 and Month 3 to measure albumin/creatinine ratio to evaluate renal function and potential injury.

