3.10.6 Additional Processing Details

Based on experience gained through processing of AKI endpoints in the recently completed ATB-202 study, the following data processing convention will be employed.

- To account for renal replacement therapy (RRT), the exact dates on which the patient is on dialysis will be determined and compared to the exact date on which the labs were drawn for the creatinine sample. If the sample was drawn within 2 days from RRT start then it was excluded from all analyses.
- If the reference creatinine is greater than 1.4, then all available creatinine values obtained on Day 10 and after, including unscheduled visits, will be evaluated. If the maximum is 1.5x the minimum, then the reference creatinine is replaced by the MDRD.
- LOCF will be used for missing Day 14 creatinine starting from Day 10.
- LOCF will be used for missing Day 28 creatinine starting from Day 7.

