4.2 Secondary Effectiveness Endpoints

The secondary effectiveness endpoints for this study are:

- Freedom from durable loss of renal function at Day 14
- Freedom from durable loss of renal function at Day 90

Reference creatinine values, baseline AKI stage and percentage loss of eGFR at Days 14 and 90 will be determined through algorithmic determination (see details above). Percentage loss of eGFR determined algorithmically will be based on a comparison of eGFR at screening compared to an algorithmically determined reference creatinine value

- Resolution of organ dysfunction (organ resolution is defined as having a total mSOFA score of ≤ 1) at Day 14
- Resolution of specific organ dysfunction (defined as having an individual organ mSOFA score of ≤ 1) at Day 14
- Critical care and hospital stay parameters
 - Hospital length of stay
 - ICU length of stay
 - ICU-free days in 28 days
 - Days on ventilator
 - Ventilator free days in 28 days
 - Vasopressor days
 - Vasopressor free days in 28 days
 - Discharge status

- Patient survival at Days 14, 28 and 90.
- Presentation of Stages 1, 2, or 3 AKI (using the KDIGO criteria)
- **Stratifications involving Day 14 mSOFA \leq 1 vs Day 14 mSOFA \geq 2**
 - Compare critical care between Day 14 mSOFA \leq 1 vs Day 14 mSOFA \geq 2
 - Compare dose groups in those with Day 14 mSOFA \leq 1
 - Compare dose groups in those with Day 14 mSOFA \geq 2
- Among patients presenting with cardiovascular failure (shock), dose group predicting Day 14 mSOFA \leq 1
- Survival to Day 90 as a function of *freedom from durable loss of renal function at 28* (overall and by dose group)

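### A missing Day 14 creatinine can be carried forward only from Day 10, a visit done only in inpatients, so patients discharged earlier have no scheduled donor value and no stated handling

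*SAP*

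**What the plan says.** SAP 4.2 lists "Freedom from durable loss of renal function at Day 14" first among the secondary endpoints, and SAP 5.3 analyses it in the same way as the primary endpoint. For missing values, SAP 3.10.6 states "LOCF will be used for missing Day 14 creatinine starting from Day 10". The next line of that section states "LOCF will be used for missing Day 28 creatinine starting from Day 7".

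Protocol 7.3 labels Visit 6 (Day 10, ±1 day) "perform only if patient is still hospitalized", and the visit table in the synopsis carries the same restriction. SAP 3.8 lists "Day 10 (creatinine only" in the chemistry schedule without repeating it, and refers to Protocol 18.1 for timing.

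Two Protocol 7.3 provisions bear on how often the gap arises. A homecare vendor is contracted to "evaluate subjects as outpatients from Day 7 through Day 90". Under Visit 7 the protocol adds: "In case a patient is discharged from hospital prior to these days SOFA parameters should be obtained on the same day of discharge". SOFA includes creatinine (Protocol Appendix C).

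SAP 5.11.2 covers missing creatinine at Days 28 and 90 but not Day 14. The statement in SAP 5.11.1 about including all randomised patients concerns the primary comparison. SAP 5.11.3 carries Day 14 mSOFA forward with no earliest donor day except that nothing is carried past death, on the ground that every patient needs a Day 14 value.

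**The concern.** Death or dialysis at Day 14 settles the endpoint without a creatinine. For everyone else a creatinine is needed, observed or carried forward. The donor floor coincides with the one early visit that only inpatients have, so two patients who both miss Day 14 are treated differently according to whether they had gone home.

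Discharge is a post-randomisation outcome, and hospital stay is itself an efficacy endpoint in SAP 4.2. The SAP states no rule for a patient without a donor, so the choice between exclusion and failure would be left to whoever programs the table, and the two choices give different answers. The plan is also inconsistent: the same Day 7 creatinine may be carried 21 days to Day 28 but not 7 days to Day 14. A creatinine drawn at discharge on Day 7 or 8 can feed the Day 14 mSOFA score but not the Day 14 renal endpoint.

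**Working it through.** **1. Who has a donor.** Take a patient who is alive, off dialysis and missing the Day 14 creatinine.

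| Situation | Scheduled value from Day 10 on? |
|---|---|
| Still an inpatient at the Day 10 visit | Yes (Visit 6) |
| Discharged on Days 10 to 13 | Yes (discharge-day SOFA creatinine) |
| Discharged on Day 9 | Perhaps, if a draw that day counts as Visit 6 |
| Discharged before Day 9 | No; the last scheduled value is Day 7 or the discharge day |

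An unscheduled value on or after Day 10 might also serve, but SAP 3.10.6 mentions unscheduled values only in its check on the reference creatinine.

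**2. The plan's own figure.** The documents give no power or evaluability figure for Day 14. The Day 28 figure reproduces: with 60 per arm, 75% versus 50%, one-sided alpha 0.05 and pooled null variance,

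power = Φ{[0.25√60 − 1.645√(2 × 0.625 × 0.375)] / √(0.75 × 0.25 + 0.50 × 0.50)} = Φ{(1.936 − 1.126) / 0.661} = 0.8897, against 0.890 in SAP Table 1.

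**3. Formulas.** For one arm, let p be the true Day 14 success rate, f the share discharged too early to have a donor, m the share of those who miss Day 14, and s the true success rate among the patients so lost. None of these is in the documents; all values below are assumptions.

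- Lost share: L = f × m
- Rate if dropped: (p − Ls)/(1 − L)
- Rate if scored as failures: p − Ls
- With m and s equal in both arms, failure scoring shrinks the difference by s × m × (f active − f placebo), which is zero if early discharge is equal.

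**4. Moderately unequal early discharge.** Assume p = 70% versus 55%, f = 50% versus 35%, s = 90%, m = 10% to 20%. Patients lost: 60 × 0.50 × m = 3 to 6 on active and 60 × 0.35 × m = 2.1 to 4.2 on placebo.

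- Dropped, m = 10%: 0.655/0.95 = 0.689 and 0.5185/0.965 = 0.537, difference 0.152.
- Dropped, m = 20%: 0.610/0.90 = 0.678 and 0.487/0.93 = 0.524, difference 0.154.
- Failures, m = 10%: 0.655 − 0.5185 = 0.1365. Failures, m = 20%: 0.610 − 0.487 = 0.123.

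Against a true 15 points, dropping gives 15.2 to 15.4. Failure scoring loses 0.9 × m × 0.15 = 1.35 to 2.7 points.

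**5. Other assumptions, with the Day 28 planning rates (75% versus 50%) borrowed for Day 14.**

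- Equal early discharge (f = 20% to 40%, m = 5% to 30%, s = 90% to 100%): 1% to 12% of patients are lost, about 1 to 14 of 120. Dropped: difference 0.253 to 0.284, power 0.892 to 0.916. Scored as failures: difference 0.250, power 0.887 to 0.871.
- Strongly unequal early discharge (f = 40% active, 20% placebo, s = 100%, m = 10% to 30%). Dropped: difference 0.250 to 0.248, power 0.877 to 0.846. Scored as failures: difference 0.230 to 0.190, power 0.828 to 0.674.

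The size of the effect depends mainly on the scoring rule that the SAP leaves out.

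**The case against.** The strongest reply is that the gap is small and the Day 10 floor defensible. Homecare exists to sample outpatients from Day 7, other accredited local laboratories are accepted, and missed visits are rescheduled, so discharge alone does not cause a missing Day 14 value. The ±1 day window and the discharge-day draw narrow the group further. SAP 3.10.6 attributes its conventions to experience in ATB-202, and a fresher donor is reasonable while creatinine may still be changing. The wider Day 28 window serves the sample-size assumption that all patients are evaluable for the primary endpoint; no such assumption is made for Day 14. A Day 7 floor alone would also leave a patient discharged before Day 7 who misses Days 7 and 14 without a donor.

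Most of this stands, and it limits the point. It does not supply the missing rule. It also does not explain why a 7-day-old value is unacceptable for Day 14 when a 21-day-old one is acceptable for the primary endpoint. Homecare is offered, not guaranteed. The unrestricted Day 10 entry in SAP 3.8 creates no sample that the protocol does not take.

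A reader might infer that the Day 14 endpoint loses its best-recovering patients and is biased against the active arm. The documents do not support that. They do not say these patients are excluded, and they give no early-discharge rate, no Day 14 miss rate and no outcome for this group. That such patients recovered well is plausible but not documented.

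**Conclusion.** The point holds as a narrow gap in a secondary endpoint. A patient alive and off dialysis who leaves hospital before the Day 10 visit window and misses Day 14 has no scheduled donor and no stated handling. An inpatient in the same position has a donor. The donor floor is out of line with the Day 28 rule and the Day 14 mSOFA rule. The primary Day 28 test is not affected.

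The size is uncertain and probably small. If these patients are dropped, in the first scenario arm rates fall by 1 to 3 points and the difference moves by less than half a point. Across the wider assumptions it stays within 0.2 points below the true value or rises, by at most 3.4 points in the extreme case. If they are scored as failures, the difference is unchanged under equal early discharge and shrinks by about 1 to 3 points under the moderately unequal scenario. A loss of 2 to 6 points needs early discharge twice as common on active, every lost patient a true success, and 10% to 30% of early-discharged patients missing the draw. A claim of material bias would need both failure scoring and unequal discharge, and the documents establish neither.

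**What to change.** In SAP 3.10.6, start Day 14 LOCF at Day 7, the floor already used for Day 28. Day 7 and later discharge-day creatinines then become eligible, and Visit 5 (Day 7) is scheduled for outpatients as well as inpatients. Keep the exclusion of samples drawn close to the start of renal replacement therapy. Add one sentence fixing, before unblinding, how a patient still without a donor is scored, since a Day 7 floor does not cover everyone. Add a Day 14 table restricted to observed values as a sensitivity analysis; it excludes more patients than the main analysis and only shows how far the result rests on carried values. If the sponsor prefers to keep Day 10, the SAP should give the reason and still state the no-donor rule.

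The cost is one changed phrase, one added sentence and one table. The downside is that a few Day 14 values will be up to 7 days old and may understate recovery, a shorter carry than the 21 days already allowed for Day 28.

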3.10.7 Alternative Algorithmic Determination of Day 28 Creatinine

If Day 28 creatinine is missing, LOCF will be used to impute Day 28 creatinine in primary analyses.

As a sensitivity analysis, the following alternative approach to determining the recovery creatinine is as follows.

1. Take all creatinine values between Day 14 and Day 28 and determine if they are consistent –if high and low value in the range are different by $>50\%$ (example 1.0 and 1.6) flag as “unstable”.
2. If unstable, take the LAST value in the range as the recovery creatinine.
3. If not unstable, take the MEAN of all values in the 14 to 28 day range as the recovery creatinine.

4 Endpoints

4.1 Primary Effectiveness Endpoint

The primary effectiveness endpoint is *freedom from durable loss of renal function at Day 28*. The primary effectiveness endpoint requires:

- (i) Alive at Day 28,
- (ii) Free of dialysis at Day 28, and
- (iii) Less than a 37% loss of estimated Glomerular Filtration Rate (eGFR; measured with the Modification of Diet in Renal Disease (MDRD) formula from the patient's reference eGFR) at Day 28.

Reference creatinine values, baseline AKI stage and percentage loss of eGFR at 28 will be determined through algorithmic determination (see details above). Percentage loss of eGFR determined algorithmically will be based on a comparison of eGFR at screening compared to an algorithmically determined reference creatinine value.

Note: The Clinical Protocol allows subjects to qualify for enrollment in terms of AKI stage through urine outcome.

